### 9.3.5. Covariates

#### Table 5.Covariates

Variable	Role	Operational definition	Measurement period
Age	Patient characteristics	
 
The number of years between the index date and the patient birth year for each time segment. Age will be reported overall and in the following categories: 65-69 years, 70-74 years, 75-79 years, 80-84 years, and 85+ years.
 
Continuous statistics including mean, standard deviation (SD), median (Q1-Q3), minimum, and maximum, will also be summarized.
 
	Baseline
Sex	Patient characteristics	Sex will be reported as Male (1), Female (2), and Unknown (0)	Baseline
Race/ethnicity	Patient characteristics	Self-reported race will be reported as White (1), Black (2), Other (3), Asian (4), Hispanic (5), North American Native (6), and Unknown (0).	Baseline
Geographic region	Patient characteristics	
 
US geographic region will be derived from the patient state and categorized into the following:
 
Northeast – Connecticut, Maine, Massachusetts, New Hampshire, Rhode Island, Vermont, New Jersey, New York, Pennsylvania
 
Midwest – Indiana, Illinois, Michigan, Ohio, Wisconsin, Iowa, Kansas, Minnesota, Missouri, Nebraska, North Dakota, South Dakota
 
South – Delaware, District of Columbia, Florida, Georgia, Maryland, North Carolina, South Carolina, Virginia, West Virginia, Alabama, Kentucky, Mississippi, Tennessee, Arkansas, Louisiana, Oklahoma, Texas
 
	Baseline

PFIZER CONFIDENTIAL

CT24-WI-GL02-RF02 6.0 Non-Interventional Study Protocol Template For Secondary Data Collection Study Page 27 of 53

		
 
West – Arizona, Colorado, Idaho, New Mexico, Montana, Utah, Nevada, Wyoming, Alaska, California, Hawaii, Oregon, Washington
 
Other/unknown – Puerto Rico/ unknown region
 
	
Respiratory season of index	Patient characteristics	The respiratory season of the individual's index date for each time segment.August 2014 – July 2015 August 2015 – July 2016 August 2016 – July 2017 August 2017 – July 2018 August 2018 – July 2019 August 2019 – November 2019	Baseline
Year of index date	Patient characteristics	The year of the individual's index date for each time segment. 2014, 2015, 2016, 2017, 2018, 2019.	Baseline
Month of index date	Patient characteristics	The month of the individual's index date for each time segment. January, February, March, April, May, June, July, August, September, October, November, or December.	Baseline
Outpatient heart failure	Patient characteristics	Any code for heart failure in the outpatient setting in the 365 days prior to the index date.	Baseline
Coronary artery disease (CAD)	Patient characteristics	Any code (any setting) for coronary artery disease (CAD) in the 365 days prior to the index date.	Baseline
Hypertension	Patient characteristics	Any code (any setting) for hypertension in the 365 days prior to the index date.	Baseline
Valvular heart disease	Patient characteristics	Any code (any setting) for valvular heart disease in the 365 days prior to the index date.	Baseline
Unstable angina	Patient characteristics	Any code (any setting) for unstable angina in the 365 days prior to the index date.	Baseline

CT24-WI-GL02-RF02 6.0 Non-Interventional Study Protocol Template For Secondary Data Collection Study Page 28 of 53

Stable angina	Patient characteristics	Any code (any setting) for stable angina in the 365 days prior to the index date.	Baseline
Aortic aneurysm and dissection	Patient characteristics	Any code (any setting) for aortic aneurysm and dissection in the 365 days prior to the index date.	Baseline
Arrhythmia	Patient characteristics	Any code (any setting) for arrhythmia in the 365 days prior to the index date.	Baseline
Atrial fibrillation	Patient characteristics	Any code (any setting) for atrial fibrillation in the 365 days prior to the index date.	Baseline
Cardiomyopathy	Patient characteristics	Any code (any setting) for cardiomyopathy in the 365 days prior to the index date.	Baseline
Peripheral arterial disease (PAD)	Patient characteristics	Any code (any setting) for peripheral arterial disease (PAD) in the 365 days prior to index	Baseline
Pulmonary hypertension	Patient characteristics	Any code (any setting) for pulmonary hypertension in the 365 days prior to the index date.	Baseline
Rheumatic heart disease	Patient characteristics	Any code (any setting) for rheumatic heart disease in the 365 days prior to the index date.	Baseline
Congenital heart defects	Patient characteristics	Any code (any setting) for congenital heart defects in the 365 days prior to the index date.	Baseline
High cholesterol	Patient characteristics	Any code (any setting) for high cholesterol in the 365 days prior to the index date.	Baseline
High triglycerides	Patient characteristics	Any code (any setting) for high triglycerides in the 365 days prior to the index date.	Baseline
Metabolic syndrome	Patient characteristics	Any code (any setting) for metabolic syndrome in the 365 days prior to the index date.	
Autoimmune disease	Patient characteristics	Any code (any setting) for autoimmune disease in the 365 days prior to index.	Baseline

CT24-WI-GL02-RF02 6.0 Non-Interventional Study Protocol Template For Secondary Data Collection Study Page 29 of 53

Transient ischemic attacks (TIA)	Patient characteristics	Any code (any setting) for TIA in the 365 days prior to index.Baseline	
Dementia	Patient characteristics	Any code (any setting) for dementia in the 365 days prior to index.	Baseline
Chronic obstructive pulmonary disease (COPD)	Patient characteristics	Any code (any setting) for COPD in the 365 days prior to index.	Baseline
Connective tissue disease	Patient characteristics	Any code (any setting) for a connective tissue disease in the 365 days prior to index.	Baseline
Peptic ulcer disease	Patient characteristics	Any code (any setting) for peptic ulcer disease in the 365 days prior to index.Baseline	
Chronic liver disease	Patient characteristics	Any code (any setting) for chronic liver disease in the 365 days prior to index.	Baseline
Diabetes mellitus	Patient characteristics	Any code (any setting) for diabetes mellitus in the 365 days prior to index.	Baseline
Hemiplegia	Patient characteristics	Any code (any setting) for hemiplegia in the 365 days prior to index.	Baseline
Solid tumor	Patient characteristics	Any code (any setting) for solid tumor malignancy within the 365 days prior to index.	Baseline
Chronic lung disease	Patient characteristics	Any code (any setting) for chronic lung disease within the 365 days prior to index.	Baseline
Asthma	Patient characteristics	Any code (any setting) for asthma within the 365 days prior to index.	Baseline
Alcoholism	Patient characteristics	Any code (any setting) for alcoholism in the 365 days prior to index.	Baseline
Smoking	Patient characteristics	Any code (any setting) for smoking in the 365 days prior to index.	Baseline
Obesity	Patient characteristics	Any code (any setting) for obesity during the 365 days prior to index.	
Functional/mobility status	Patient characteristics	A procedure code indicating decreased functional status or mobility in the 365 days prior to index.	Baseline

CT24-WI-GL02-RF02 6.0 Non-Interventional Study Protocol Template For Secondary Data Collection Study Page 30 of 53

Physical/wellness visit	Patient characteristics	A CPT or diagnosis code for a wellness visit in the 365 days prior to index.	Baseline
Number of hospitalizations in the prior 180d	Patient characteristics	
 
Count of unique days with an acute hospital admission in the 180 days prior to index
 
Dichotomous, yes/no
 
Continuous statistics including mean, standard deviation (SD), median (Q1 Q3), minimum, and maximum
 
	Baseline
Number of outpatient visits in the prior 180d	Patient characteristics	Count unique days with an outpatient visit in the 180 days prior to index	Baseline
		
 
Dichotomous, yes/no
 
Continuous statistics including mean, standard deviation (SD), median (Q1 Q3), minimum, and maximum
 
	
Nursing home stay	Patient characteristics	Any claim with care location of nursing home in the 365 days prior to index.	Baseline
Skilled nursing facility (SNF) stay	Patient characteristics	Any claim with care location of SNF in the 365 days prior to index.	Baseline
Influenza vaccine	Patient characteristics	Baseline influenza vaccination status: One claim (NDC or CPT) for influenza vaccine of any type in the 365d prior to index.	Baseline and follow-up
		Time-varying influenza vaccination status during follow-up : Patients will be identified and can transition between periods of influenza vaccine exposure and non-exposure throughout the study period. Individuals will be classified as vaccinated starting 15 days after their first claim for an influenza vaccine during each respiratory season and considered vaccinated until the end of that respiratory season.	

CT24-WI-GL02-RF02 6.0 Non-Interventional Study Protocol Template For Secondary Data Collection Study Page 31 of 53

		The 1-year mediation analysis will adjust for baseline influenza vaccination status only.	
Type of index influenza vaccine administered	Patient characteristics	Categories include: Enhanced, standard, and unknown influenza vaccine type	Baseline
PPSV23 receipt	Patient characteristics	One claim (NDC or CPT) for a PPSV23 vaccine between 1 year and 5 years prior to the index date.	Baseline
Respiratory failure	Patient characteristics	Any code (any setting) within the prior 365 days for respiratory failure. Prior respiratory failure will be included as a descriptive variable only.	Baseline
Influenza infection	Patient characteristics	≥1 ICD-9-CM or ICD-10-CM code for influenza in 365 days prior to index	Baseline
Outpatient pneumonia	Patient characteristics	≥1 ICD-9-CM or ICD-10-CM code for pneumonia in the outpatient setting in the 365 days prior to index.	Baseline
Telehealth visits	Patient characteristics	
 
Count of unique days with telehealth visit in the 365 days prior to index.
 
Dichotomous, yes/no
 
Number categories: 0, 1, 2+
 
Continuous statistics including mean, standard deviation (SD), median (Q1 Q3), minimum, and maximum
 
	Baseline
Flu test in the prior 365 days		Influenza test ordered in the 365 days prior to index. • Dichotomous, yes/no	Baseline
Number of labs ordered in the prior 365 days	Patient characteristics	
 
Count of unique days with any lab ordered in the 365 days prior to index
 
Dichotomous, yes/no
 
Number categories: 0, 1, 2+
 
	Baseline

CT24-WI-GL02-RF02 6.0 Non-Interventional Study Protocol Template For Secondary Data Collection Study Page 32 of 53

		• Continuous statistics including mean, standard deviation (SD), median (Q1 Q3), minimum, and maximum	
Number of lipid lab tests ordered in the prior 365 days	Patient characteristics	
 
Count of unique days with a lipid lab ordered in the 365 days prior to index
 
Dichotomous, yes/no
 
Number categories: 0, 1, 2+
 
Continuous statistics including mean, standard deviation (SD), median (Q1 Q3), minimum, and maximum
 
	Baseline
Echocardiogram	Patient characteristics	
 
Count of unique days with an echocardiogram procedure code in the 365 days prior to index.
 
Dichotomous, yes/no
 
Number categories: 0, 1, 2+
 
Continuous statistics including mean, standard deviation (SD), median (Q1 Q3), minimum, and maximum
 
	Baseline
Electrocardiogram	Patient characteristics	
 
Count of unique days with an electrocardiogram procedure code in the 365 days prior to index.
 
Dichotomous, yes/no
 
Number categories: 0, 1, 2+
 
Continuous statistics including mean, standard deviation (SD), median (Q1 Q3), minimum, and maximum
 
	Baseline

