	Assuming an average follow-up duration of 3 years, the study will require a minimum sample size of 9,600 adults. Assuming an average follow-up duration of 0.75 years, the study will require a minimum sample size of 36,485 adults.
	A feasibility analysis using the Medicare fee-for-service claims database estimated approximately 25 million adults are eligible for inclusion in the study during the years of interest.
Data analysis	Separate analyses will be conducted with 0 to 1 year and 0 to 3 years of follow-up. A cause-specific Cox proportional hazards model with time-varying covariates will be used for the primary analysis. The cause-specific cox model will be used to estimate hazard ratios (HRs) for each MACE outcome, comparing PCV13 vaccinated with PCV13 unvaccinated Medicare enrollees. The weighted cumulative incidence function (CIF) will also be presented, describing and accounting for competing risk events. The analysis will utilize Inverse Probability of Treatment Weighting (IPTW) to adjust for baseline differences between the vaccinated and unvaccinated cohorts. Covariates with residual imbalance after weighting will be included in the final models for further adjustment to control for potential confounders. The primary analysis models will also adjust for influenza vaccination status during follow-up as a time-varying covariate.
	The study will also include a mediation analysis, which is considered a secondary analysis. The mediation analysis will estimate the direct and indirect effects of PCV13 receipt on MACE, examining the extent to which the relationship between PCV13 and MACE within 1 year of follow-up is mediated by CAP. The mediation analysis will utilize the product method,  which uses a logistic weighted mediation model to assess the mediator and a Cox model weighted outcome model to derive the HR and confidence intervals (CI).
	The study will also include three sensitivity analyses. The first sensitivity analysis will incorporate the Fine-Gray model, which provides an alternative to the cause-specific Cox model and helps ensure the robustness of the findings when comparing different analytical approaches to competing risks. Second, the study will include a sensitivity analysis using an alternative definition of stroke. The primary analysis

CT24-WI-GL02-RF02 6.0 Non-Interventional Study Protocol Template For Secondary Data Collection Study Page 11 of 53

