- Individuals with Medicare Part C enrollment between September 14, 2014 and the index date were excluded because the individual would have been eligible to receive PCV13, but any vaccination records during enrollment in Medicare Part C would not be included in the individual's Medicare FFS records. As such, these individuals were excluded to reduce the risk of misclassifying PCV13 vaccination status.
- PCV13 vaccinated individuals with a pneumonia diagnosis code in the hospital setting or a MACE diagnosis code in the hospital, SNF, or LTCF setting in the 13 days after first PCV13 vaccination because the vaccine is not considered to be fully effective until 14 days following vaccination.

Exclusion criteria: Sample size impact

• Approximately 25 million individuals are estimated to be eligible for inclusion in the study. As such, these exclusion criteria do not substantially impact the ability to meet the minimum sample size required for this study. Please refer to **Section 9.5** for additional information on the minimum sample size required for this study.

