## 9.5. Study Size

To determine the appropriate sample size for our study, we conducted a power analysis based on logrank test. The analysis was designed to evaluate the effect of PCV13 vaccination on the risk of first event MACE, with the following key assumptions:

- Treatment-to-control group allocation ratio: Based on the feasibility study using data from September 14, 2014, to December 31, 2019, the proportion of the vaccinated group is 39.6%. Consequently, the treatment-to-control group allocation ratio was set to 2:3.
- Hazard ratio (HR): We assumed a hazard ratio of 0.85 for the vaccinated group compared to the unvaccinated group, indicating a 15% reduction in the risk of first event MACE associated with PCV13 vaccination. Another scenario with an HR of 0.8 is also provided.
- Hazard rate for control group: Based on the above feasibility study, the 5-year overall event probability was 21.2%. Consequently, we calculated the hazard rate for the control group to be 0.0507. This calculation was derived from the pre-assumed HR of 0.85, the overall 5-year survival probability, and the treatment-to-control group allocation ratio. For the scenario with HR=0.8, the corresponding hazard rate for the control group is 0.0518.
- Follow-up time: In this study, not all patients will complete the full duration of follow-up due to censoring events such as vaccination status switching or death. To account for this in the sample size calculation, we adjusted the calculation using shorter average follow-up periods. Specifically, we considered four follow-up durations: 1-year, 0.75 year, 3 years, and 2.75 years.
- Statistical power: 80%.
- Test was two-sided with significance level (α): 0.05, which corresponds to a 5% chance of a Type I error.

The required total sample sizes for each scenario were determined as follows to achieve a 80% power:

Hazard Ratio	Control Group Hazard Rate	Follow-up time in	Total N Required
		years	
0.85	0.0507	1	27,520
		0.75	36,485
		3	9,600
		2.25	12,585

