#### PFIZER CONFIDENTIAL

CT24-WI-GL02-RF02 6.0 Non-Interventional Study Protocol Template For Secondary Data Collection Study Page 35 of 53 0.1 will be considered as balanced. Stabilized weights will be used to limit the impact of outliers and truncation at the 1st and 99th percentiles may be considered. Covariates with residual imbalance after weighting will be included in the final models for further adjustment to control for potential confounders. Depending on the balance checks for censoring status within the IPTW-weighted population, IPTW may be combined with inverse probability of censoring weighting (IPCW) to address potential issues of informative censoring. IPCW adjusts for potential biases due to censoring, with weights calculated based on the probability of censoring at various time points.

Only baseline covariates will be adjusted for using IPTW. Time-varying influenza vaccination status will be adjusted for directly in the Cox proportional hazards models for the primary outcomes analysis. Individuals will be classified as vaccinated starting 15 days after their first claim for an influenza vaccine during each respiratory season and considered vaccinated until the end of that respiratory season. The Cox model will treat influenza vaccination as a time-varying variable using a counting process. Baseline covariates included in the PS models for IPTW and IPCW will be finalized based on their clinical and statistical importance and will be detailed in the SAP.

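### Geography is defined only as four regions plus Other/unknown although state is in hand, so state differences within a region that other covariates do not explain go unadjusted and unseen.

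*Protocol*

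**What the plan says.** Section 9.3.5, Table 5, has one geography row: "US geographic region will be derived from the patient state and categorized into the following". It lists four named regions and a fifth level, "Other/unknown – Puerto Rico/ unknown region". The South row holds 16 states and the District of Columbia. No row is defined at state level or below, and none covers income, deprivation or rurality.

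Section 9.7 (Balancing and Covariate Adjustment Methods) builds the propensity score by logistic regression and checks balance with standardized mean differences, where an absolute value up to "0.1 will be considered as balanced". Covariates still imbalanced after weighting go into the outcome models. The covariate list is not final: "Baseline covariates included in the PS models for IPTW and IPCW will be finalized based on their clinical and statistical importance", with details left to the SAP.

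On size, the Abstract reports that "approximately 25 million adults are eligible for inclusion in the study during the years of interest". Section 9.5 says that "the proportion of the vaccinated group is 39.6" percent and that "the treatment-to-control group allocation ratio was set to 2:3".

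**The concern.** A five-level region variable balances the regional mix of the two cohorts but not the state mix inside each region. If, within a region, states with higher PCV13 uptake also have lower or higher MACE rates, or code these diagnoses differently, part of that difference would pass into the hazard ratio. The balance check and the residual-imbalance step act only on covariates that have been defined, so neither would show it.

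Scale is what makes this worth raising. With about 25 million eligible people, random error almost vanishes and systematic error decides how the result is read. A bias too small to notice in an ordinary study could give a confidence interval that excludes 1. The value needed to reduce the risk is already read for every person.

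**Working it through.** **1. The plan's own figures.** Solving 0.4·exp(−0.85·5h) + 0.6·exp(−5h) = 1 − 0.212 gives h = 0.0507, the control hazard in Section 9.5. A Lakatos-type log-rank calculation with 2:3 allocation and 80% power gives 36,552 for 0.75 years and 27,571 for 1 year, against the stated 36,485 and 27,520 (within 0.2%). The planning inputs can therefore be used below.

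**2. Random error at the expected size.** The event probability over 1 year is 0.4·(1 − exp(−0.85·0.0507)) + 0.6·(1 − exp(−0.0507)) = 0.0465. Times 25 million, that is about 1.163 million events. The SE of the log HR is 1/√(1,163,339·0.4·0.6) = 0.0019, so the 95% half-width is about 0.0037. With 0.75 years the event probability is 0.0351 and the SE 0.0022; with 3 years, 0.1332 and 0.0011. These ignore the extra variance from weighting and from people who contribute two segments.

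**3. Possible shift in a null hazard ratio.** With p = 0.396, p(1 − p) = 0.396·0.604 = 0.2392. For a state factor left unadjusted within region,

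shift in log HR ≈ correlation · SD(uptake) · SD(log rate) / 0.2392.

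All three inputs are assumptions; the Protocol gives none of them.

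| | Uptake SD | Log-rate SD | Absolute correlation | Shift in log HR | Null HR reads |
|---|---|---|---|---|---|
| Low | 0.04 | 0.08 | 0.3 | ±0.0040 | 0.996 or 1.004 |
| Middle | 0.06 | 0.115 | 0.45 | ±0.0130 | 0.987 or 1.013 |
| High | 0.08 | 0.15 | 0.6 | ±0.0301 | 0.970 or 1.031 |

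The sign follows the sign of the correlation. At the high end a true 0.85 would read 0.85·0.970 = 0.825 or 0.85·1.031 = 0.876. A direct simulation agrees with the formula: uptake SD 0.04, log-rate SD 0.10 and correlation −0.6 give 0.990 both ways. A second grid (uptake SD 0.02 to 0.06, log-rate SD 0.05 to 0.15, correlation −0.3 to −0.9) gives 0.999 to 0.966.

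**4. What adjustment costs.** Table 5 lists 9 + 12 + 17 + 13 = 51 jurisdictions. Replacing 4 regions by 51 jurisdictions adds 51 − 4 = 47 parameters, or about 1,163,339/47 = 24,750 events each at 1 year. Approximate variance inflation is 1/(1 − SD²/0.2392): 1.007 at an uptake SD of 4 points, 1.015 at 6, 1.027 at 8 and 1.044 at 10. Even at 10 points the largest minimum sample size would move only from 36,485 to about 38,080.

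**5. Would a balance table by state be enough?** Take a state with 1/51 of the population. If its uptake is 4 points above 39.6%, it holds 2.16% of vaccinated and 1.83% of unvaccinated people, a standardized difference of about 0.02. At 8 points above, the shares are 2.36% and 1.70%, and the difference about 0.05. A state with 5% of the population and uptake 8 points above reaches about 0.08. All pass the 0.1 limit, so a check by state would often flag nothing. State has to be placed in the model beforehand.

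**The case against.** The strongest objection is that Section 9.7 leaves the final propensity-score covariates to the SAP, so nothing rules out state. That is correct, and the SAP may already include it. But Table 5 fixes a concrete coding of geography, and no candidate variable finer than region is defined for the SAP to choose from.

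Second, more than 50 other covariates are listed, among them race, smoking, diabetes, lipids, prior influenza and PPSV23 vaccination, and measures of care use. They may explain much of why states differ in uptake and MACE. This stands: the shifts above are before any such adjustment, and the high end needs all three inputs at their extremes.

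Third, region is a recognised choice, residual confounding is acknowledged in Section 9.9, and two negative control outcomes are planned. This stands in part. The controls can signal bias but do not remove it, and cataract surgery and lipoma need not follow the same state pattern as MACE.

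A reader might infer that state differences do confound the comparison, or that they favour the vaccine. The Protocol supports neither: it holds no state-level uptake, MACE or coding figures, and a positive correlation would reverse the direction.

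**Conclusion.** The point holds as a refinement, not as a demonstrated error. State is read and then discarded in favour of five levels, and the planned safeguards cannot see what is lost. The possible shift of 0.4% to 3% in either direction rests wholly on the assumed inputs and is an unadjusted figure. Against the assumed 15% reduction it is small. Against a standard error of about 0.002 it runs from about two to about sixteen standard errors (0.0040/0.0019 to 0.0301/0.0019), so it could matter for a result near the null. Comparison with so small a standard error would make many modest biases look important; the case for acting rests mainly on the low cost. The sample size calculation is not affected.

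**What to change.** Add state to Table 5, with all levels plus territory/unknown, as a covariate for the IPTW model, and keep region for the descriptive tables. A Cox model stratified by state is an alternative. The propensity model is the better place, because the weights also serve the weighted cumulative incidence curves and the weighted mediation models, which a Cox stratum does not reach. Report weighted balance by state for information, without relying on the 0.1 limit to bring state in. If region is kept in the main model, prespecify a state-adjusted sensitivity analysis.

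The cost is a line in Table 5 and the SAP, about 47 parameters, and variance inflation of roughly 1% to 3% for an uptake SD of 4 to 8 points. Adjustment is almost free, not entirely free. Descriptive tables can stay at region level. A balance summary by state can be exported as standardized differences, without counts, so the small-cell rule in Section 9.6 need not stand in the way.

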	Covariates: Age, Sex, Race/ethnicity, Geographic region, Respiratory season of index, Year of index date, Month of index date, Outpatient heart failure, Coronary artery disease (CAD), Hypertension, Valvular heart disease, Unstable angina, Stable angina, Aortic aneurysm and dissection, Arrhythmia, Atrial fibrillation, Cardiomyopathy, Peripheral arterial disease (PAD), Pulmonary hypertension, Rheumatic heart disease, Congenital heart defects, High cholesterol, High triglycerides, Metabolic syndrome, Autoimmune disease, Transient ischemic attacks (TIA), Dementia, Chronic obstructive pulmonary disease (COPD), Connective tissue disease, Peptic ulcer disease, Chronic liver disease, Diabetes mellitus, Hemiplegia, Solid tumor, Chronic lung disease, Asthma, Alcoholism, Smoking, Obesity, Functional/mobility status, Physical/wellness visit, Number of hospitalizations in the prior 180d, Number of outpatient visits in the prior 180d, Nursing home stay, Skilled nursing facility (SNF) stay, Influenza vaccine, Type of index influenza vaccine administered, PPSV23 receipt, Respiratory failure, Influenza infection, Outpatient pneumonia, Telehealth visits, Flu test in the prior 365 days, Number of labs ordered in the prior 365 days, Number of lipid lab tests ordered in the prior 365 days, Echocardiogram, Electrocardiogram

CT24-WI-GL02-RF02 6.0 Non-Interventional Study Protocol Template For Secondary Data Collection Study Page 10 of 53

Data source	The Medicare administrative claims database includes individuals $\geq$ 65 years of age and individuals with a qualifying disability who are enrolled in a Medicare fee-for- service plan. The database includes enrollment information for these individuals as well as adjudicated claims for inpatient care, ambulatory care, and outpatient prescriptions.
Study size	Treatment-to-control group allocation ratio (2:3) and the hazard rate for the control group (0.0507) were estimated based on a feasibility analysis using the Medicare fee-for-service claims database. We assumed a hazard ratio of 0.85 for the PCV13 vaccinated compared to the unvaccinated group and used a two-sided test with a significance level of 5%. To account for different follow-up durations, we calculated required sample sizes for average follow-up durations of 0.75, 1, 2.75, and 3 years. The sample sizes were calculated to achieve 80% power in each scenario.

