#### PFIZER CONFIDENTIAL

CT24-WI-GL02-RF02 6.0 Non-Interventional Study Protocol Template For Secondary Data Collection Study Page 17 of 53 Exclusion criteria rationale:

- Individuals with evidence of PCV13 vaccination prior to the index date were excluded because the individual would not be eligible to receive a PCV13 vaccine during the study period
- Individuals with evidence of PPSV23 vaccination in the 365 days prior to the index date were excluded because PPSV23 receipt within 365 days prior to PCV13 receipt could result in hyporesponsiveness to the PCV13 vaccine. In addition, the CDC ACIP PCV13 receive a dose of PCV13 if the individual had not previously received a pneumococcal vaccine or if the individual received PPSV23 ≥1 year prior. This exclusion criterion was included to align with the CDC ACIP recommendations at the start of the study period.
- The CDC ACIP recommended PCV13 for adults age ≥19 years with a high-risk condition for pneumonia on October 12, 2012. Individuals with ≥1 diagnosis code for a pneumonia high-risk condition in the 365 days prior or evidence of iatrogenic immunosuppression in the 6 months prior to index were excluded because these individuals were eligible to receive PCV13 prior to turning age 65 years and before being eligible to enroll in Medicare health insurance. Since records of vaccination prior to enrolling in Medicare are not available in the database, these individuals were excluded to reduce the risk of misclassifying PCV13 vaccination status.
- Individuals with a pneumonia diagnosis code in the hospital setting in the 365 days prior to the index date were excluded because recent history of severe pneumonia increases the risk of a future diagnosis of pneumonia. Pneumonia is the hypothesized mediator for the impact of PCV13 on risk of MACE. Excluding these individuals equalizes this risk for the PCV13 vaccinated and PCV13 unvaccinated cohorts.
- Individuals with a MACE diagnosis code in the hospital, SNF, and LTCF setting the 365 days prior to the index date were excluded because recent history of an acute MACE event increases the risk of a future MACE event. Excluding these individuals equalizes this risk for the PCV13 vaccinated and PCV13 unvaccinated cohorts.

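### Table 5 measures prior respiratory failure at baseline but restricts it, without a reason, to description, so a plausible confounder already being derived cannot enter the weights or the outcome model

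*Protocol*

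**What the plan says.** Section 9.3.5, Table 5, defines the variable as "Any code (any setting) within the prior 365 days for respiratory failure", gives its measurement period as baseline, and adds: "Prior respiratory failure will be included as a descriptive variable only". None of the other rows carries such a limit.

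Section 9.7 (Balancing and Covariate Adjustment Methods) describes how baseline variables are adjusted for:

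- On the weighting: "Only baseline covariates will be adjusted for using IPTW".
- On the choice of variables: "Baseline covariates included in the PS models for IPTW and IPCW will be finalized based on their clinical and statistical importance", with the detail left to the SAP.
- On what weighting leaves behind: "Covariates with residual imbalance after weighting will be included in the final models for further adjustment to control for potential confounders". The threshold is an absolute standardized mean difference (SMD) of 0.1.

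The abstract (Section 4, Variables) places respiratory failure in its covariate list with no restriction: "PPSV23 receipt, Respiratory failure, Influenza infection, Outpatient pneumonia".

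Section 9.2 explains the exclusion of recent hospital pneumonia by saying that "recent history of severe pneumonia increases the risk of a future diagnosis of pneumonia", and explains the exclusion of recent facility-coded MACE by a parallel argument about future MACE.

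**The concern.** A respiratory failure code before index cannot be a consequence of the vaccination under study, so it is not a mediator of PCV13. It plausibly marks recent severe cardiorespiratory illness. Such illness may make vaccination less likely and may raise the risk of both pneumonia and MACE. The protocol reasons in the same way when it excludes recent hospital pneumonia and recent MACE, and its section on negative control outcomes names healthy-vaccinee behaviour as a source of residual confounding.

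Section 9.7 would normally let such a variable into the propensity score on clinical grounds, or into the outcome model if it stayed imbalanced. The sentence in Table 5 takes both options away in advance, whatever the data show. If the variable does confound, the residual bias would pass into the primary and secondary hazard ratios and, through the weights, into the mediation models.

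**Working it through.** **1. Is the variable closed off?** Table 5 fixes its role as descriptive. Section 9.7 has two routes to adjustment, the propensity score model and the residual-imbalance rule. A variable that is descriptive only can use neither. Section 9.7 leaves the selection of covariates to the SAP, but for this one variable the protocol has already decided.

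**2. What already covers it?**

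- Section 9.2.2 excludes, over 365 days, hospital pneumonia codes, MACE codes in hospital, SNF or LTCF, and high-risk conditions. It also excludes iatrogenic immunosuppression over 6 months.
- Table 5 lists COPD, chronic lung disease, asthma, pulmonary hypertension, outpatient heart failure, outpatient pneumonia, influenza infection, hospitalizations in the prior 180 days, SNF and nursing home stays, and functional status.
- A gap remains. For example, an episode 181 to 365 days before index without a pneumonia or MACE code falls outside those two exclusions and outside the hospitalization count.

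**3. How large could the bias be?** The protocol gives no prevalence of respiratory failure and no risk ratio for MACE, so every input here is an assumption. For one binary confounder with prevalence p_v in the vaccinated and p_u in the unvaccinated, and a hazard ratio R for MACE, the estimated hazard ratio is multiplied by approximately

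(1 + p_v(R − 1)) / (1 + p_u(R − 1)).

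| Unvaccinated v vaccinated | R = 2 | R = 3 | SMD |
|---|---|---|---|
| 1% v 0.7% | 1.007/1.010 = 0.997 | 1.014/1.020 = 0.994 | 0.03 |
| 2% v 1.5% | 1.015/1.020 = 0.995 | 1.030/1.040 = 0.990 | 0.04 |
| 2% v 1% | 1.010/1.020 = 0.990 | 1.020/1.040 = 0.981 | 0.08 |
| 3% v 2% | 1.020/1.030 = 0.990 | 1.040/1.060 = 0.981 | 0.06 |

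These are raw prevalences. Weighting on correlated covariates would shrink the gaps, so the factors are nearer to upper bounds for these inputs.

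**4. Against the planned effect.** 0.85 × 0.997 = 0.847 and 0.85 × 0.981 = 0.834.

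**5. Against random error.** The inputs come from Section 9.5 (control hazard 0.0507 per year, hazard ratio 0.85, allocation 2:3, 0.75 years of follow-up) and Section 9.2 (about 25 million eligible). As a check on the Section 9.5 inputs, the protocol's total of 27,520 for 1 year is reproduced closely: 27,600 by Freedman's formula and 27,571 by Lakatos's.

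- Event probability at 0.75 years: 0.6 × (1 − e^(−0.0507×0.75)) + 0.4 × (1 − e^(−0.0507×0.85×0.75)) = 0.6 × 0.0373 + 0.4 × 0.0318 = 0.0351.
- At 25 million: about 878,000 events. The 95% half-width on the log hazard ratio is 1.96/√(878,000 × 0.24) = 0.0043, or about 0.43%.
- At an assumed 5 million: about 176,000 events, half-width 0.0095, or about 1%.

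The biases in step 3 run from 0.3% to 1.9%. At 25 million all but the smallest (0.3%) exceed the half-width. At 5 million three are smaller (0.3%, 0.5%, 0.6%), three are about equal (1.0%), and two are larger (1.9%). These half-widths ignore weighting, which would widen them.

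**The case against.** The case against is substantial.

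- **Confounding is inferred.** Nothing in the protocol ties respiratory failure itself to vaccine uptake or to MACE. The argument in Section 9.2 concerns pneumonia and MACE, and applying it here is an analogy. The direction is open too: people with chronic lung disease and frequent care contact might be vaccinated more often. This stands, and the variable can only be called a plausible confounder.
- **Much of the signal is already controlled.** The exclusions and listed covariates leave only respiratory failure that none of them explains. This stands, and it limits the size.
- **The SAP decides the covariates and may modify the protocol.** This is true in general, and baseline tables after weighting would show an imbalance. It does not answer the point, because the protocol itself fixes the role of this variable.

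Three stronger readings are tempting and are not supported. A reader might infer that the primary hazard ratio is known to be biased in favour of PCV13; the documents establish neither the bias nor its direction. A reader might infer that the bias generally matches or exceeds the random error; several of the scenarios fall below it, and the half-widths come from this check, not from the protocol. A reader might also take the abstract to contradict Table 5; the abstract only lists variables and says nothing about how each is used.

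The small SMDs in the table show that a rare variable can differ between groups and still pass the 0.1 threshold. That is true of any rare variable, and the threshold applies after weighting, so it is not evidence about this row in particular.

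**Conclusion.** The point holds in a limited form. One pre-index variable, already derived, is barred from adjustment without a reason, and this sits poorly with the selection and imbalance rules in Section 9.7. Under the assumed prevalences and a MACE hazard ratio of 2 to 3, the effect on the hazard ratio is a factor of about 0.997 to 0.981 before related covariates absorb part of it. That could not by itself produce a 15% reduction. It deserves attention because, with up to 25 million people, random error is so small that modest systematic errors can be comparable to it. The expected direction, towards apparent benefit, rests on sicker people being vaccinated less often, which the documents do not show. The change is worth considering because it costs almost nothing, not because a large bias has been demonstrated.

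**What to change.** In Table 5, delete the sentence that limits prior respiratory failure to description. Treat the variable like the other 365-day comorbidities: include it in the propensity score model for IPTW, in the IPCW model if that is used, and in the balance table. It then reaches the mediation analysis through the weights. If there is a reason to leave it out, state that reason, report its SMD after weighting, and add a sensitivity analysis that includes it. The cost is one line in Table 5 and one entry in the SAP covariate list. No new data are needed, and the required sample size does not change.
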